9.5.2 Currently Corrected Distance Visual Acuity

Currently corrected distance visual acuity will be measured for each eye using the provided distance logarithmic visual acuity chart for testing at 3 meters at visits. The total number of letters read correctly at each visit will be summarized with descriptive statistics by treatment group.

Frequency tables based on the change from baseline in total number of letters read correctly will be provided at each visit for the following categories:

- 3 lines or better than baseline ("Much Better")
- 2 lines better than baseline ("Better")
- Between 1 line worse and 1 line better than baseline ("No change")
- 2 lines worse than baseline e ("Worse")
- 3 lines or worse than baseline ("Much Worse")

9.5.3 Best Corrected Distance Visual Acuity

BCVA is measured via subjective refraction for each eye using the provided distance logarithmic visual acuity chart for testing at 3 meters at Screening (Day -7) and Day 90/Early Exit visits. BCVA will be summarized same way described for currently corrected distance visual acuity in Section 9.5.2.

9.5.4 Intraocular Pressure

IOP is measured for each eye using the Goldmann applanation tonometer at each visit. Baseline IOP and change from baseline IOP will be summarized with descriptive statistics by treatment group for participants with glaucoma or ocular hypertension (OHT).

10.0 Other Analyses

10.1.1 Pharmacokinetics/Pharmacodynamics

Pharmacokinetics/pharmacodynamics parameters are not evaluated in this study.

10.1.2 Genetics

Genetics are not evaluated in this study.

11.0 Interim Analyses

No interim analysis is planned for this study.

11.1 Data Monitoring Committee

Data monitoring committee is not required for this study.

12.0 Overall Type-I Error Control

To control the family-wise type I error rate at 0.05 for multiplicity across the hypothesis tests, a hierarchical gatekeeping procedure will be followed.

Step 1: Test the noninferiority hypothesis. If the upper limit of the 2-sided 95% CI is less than 2.3 units, reject H_0 and go to Step 2. Otherwise stop.

Step 2: Test the superiority hypothesis.

13.0 SAP Version History

This SAP is based on the Protocol 2007-301-005 Amendment 2 dated 08 Jun 2020.

SAP Version History Summary			
SAP Version	Approval Date	Change	Rationale
1	07 JAN 2021	Not Applicable	Original version
Amendment 1	02 Aug 2021		Amendment 1

Appendix A. Protocol Deviations

Protocol deviations will be defined in Protocol Deviation Requirement Specification, including importance classification. The number and percentage of participants with significant protocol deviations that occurred in the randomized treatment period will be summarized by treatment group for ITT population.

Appendix B. Safety Assessments

1. Slit-Lamp Biomicroscopy

Slit-lamp biomicroscopy (*without* pupil dilation) will be performed on both eyes at all visits during the study.

The following will be examined at each visit:

- Eyelid/eyelid margins/lashes
- Conjunctiva
- Cornea
- Anterior chamber

Findings other than those listed above will be recorded under "other" for the appropriate location of the finding.

EYELID / EYELID MARGINS / LASHES

Erythema

0	(None)	No erythema
+0.5	(Trace)	Localized, minimal (trace) flush reddish color
+ 1	(Mild)	Localized, mild, flush reddish color
+ 2	(Moderate)	Diffuse reddish color encompassing the entire lid margin
+ 3	(Severe)	Deep diffuse reddish color of lid margins and superior and/or inferior eyelid

Edema (eyelids)

0	(None)	No edema
+ 0.5	(Trace)	Localized, minimal (trace) swelling
+ 1	(Mild)	Localized, mild swelling
+ 2	(Moderate)	Diffuse, moderate swelling
+ 3	(Severe)	Diffuse, severe swelling

CONJUNCTIVA (BULBAR AND PALPEBRAL)

Hyperemia

0	(None)	No hyperemia
+0.5	(Trace)	Minimal (trace) flush, reddish color
+ 1	(Mild)	Mild flush, reddish color
+ 2	(Moderate)	Bright red color
+ 3	(Severe)	Deep, bright diffuse redness

Edema

0	(None)	No edema
+0.5	(Trace)	Localized, minimal (trace) swelling
+ 1	(Mild)	Localized, mild swelling
+ 2	(Moderate)	Diffuse, moderate swelling
+ 3	(Severe)	Diffuse, severe swelling

CORNEA

Edema

0	(None)	No edema
+0.5	(Trace)	Localized, minimal (trace) epithelial haze
+ 1	(Mild)	Dull glass appearance of epithelium that may include fine localized microcystic changes
+ 2	(Moderate)	Dull glass appearance of epithelium with large number of cystic changes with or without stromal edema

Epithelial bullae and/or stromal edema, localized or diffuse, with or +3 (Severe) without stromal striae

ANTERIOR CHAMBER

Cells

0	=	0 cells
+ 0.5	=	1 to 5 cells (trace)
+ 1	=	6 to 15 cells
+ 2	=	16 to 25 cells
+ 3	=	26 to 50 cells
+ 4	=	> 50 cells
Flare		
0	=	None: no flare seen
. 1		\mathbf{F} : \mathbf{c} : \mathbf{c}

+ 1	=	Faint: faint flare seen

+2Moderate: iris and lens details clear =

+ 3 = Marked: iris and lens details hazy

+4 = Intense: fibrin or plastic aqueous

2. Currently Corrected Distance Visual Acuity

At all visits, corrected visual acuity will be measured using a logarithmic visual acuity chart with Sloan letters for testing at 3 meters (9 feet, 10 inches).

Begin by first testing the right eye. Occlude the left eye. The participant should be asked to start on the top line of the bottom right chart (20/50 equivalent). Participants should be told to read the letters from left to right on each line and that the chart has letters only, no numbers. If the participant reads a number, he/she should be reminded that the chart contains no numbers, and the examiner should then request a letter in lieu of the number.

The participant should be asked to read slowly to achieve best identification of each letter and not to proceed to the next letter until he/she has given a definite answer.

If the participant changes a response (eg, "that was a C not an O") before he/she has read aloud the next letter, then the change must be accepted. If the participant changes a response after having read the next letter, then the change will not be accepted. The examiner must not point to specific letters during the test.

When the letters become difficult to read, or if the participant identifies a letter as one of 2 letters, he/she should be asked to choose one letter and, if necessary, to guess. Participants should be encouraged to continue trying even when letters become difficult to read. Stop testing when 3 or more errors are made on the same line. Use the supplied source document worksheet to mark the letters missed for each line and to enter the number of letters correctly read for each line.

If a participant cannot read the 20/50 equivalent line when instructed, verify that the proper current correction is in place. If the participant is still unable to read the 20/50 equivalent line, have him/her read from the top of the full center chart, letter by letter, and record the number of letters missed and the number of letters correctly read for each line in the source document.

Test the left eye following the same procedures outlined above, except have the participant start on the top line of the bottom left chart (20/50 equivalent). This strategy minimizes letter memorization.

3. BCDVA

Best-corrected visual acuity will be measured at Day -7 (Screening) and Day 90/Early Exit visits using the same logarithmic visual acuity chart with Sloan letters for testing at 3 meters (9 feet, 10 inches) that will be used for the currently corrected distance visual acuity. The LogMar chart will be viewed using a trial frame holding the best-corrected

distance endpoint manifest refraction. (Measuring acuity using the phoropter is acceptable so long as the chart distance is 3 meters.)

Sphere, cylinder, and axis will be determined, and a consistent endpoint should be used, which is generally the least minus sphere that provides the participant's best measured acuity. Visual acuity should be determined using the same procedure used for currently corrected distance visual acuity. The phoropter may be either a plus or minus cylinder design. Values generated should be recorded directly from the phoropter without conversion.

4. IOP (participants with glaucoma or OHT only)

After the Schirmer test with anesthetic is administered, IOP will be measured for each eye at Screening (Day -7) and Baseline (Day 1) and at all scheduled visits for participants with glaucoma or OHT only.

Measurements should be taken using a Goldmann applanation tonometer affixed to a slit-lamp with the participant seated. Additional sodium fluorescein can be applied if needed. Both eyes will be tested, with the right eye preceding the left eye. The measurer looks through the binocular viewer of the slit lamp at low power. The tension knob is preset at low pressure value (4 to 6 mm Hg). The measurer follows the image of the fluorescein-stained semicircles while he/she slowly rotates the tension knob until the inner borders of the fluorescein rings touch each other at the midpoint of their pulsation in response to the cardiac cycle. When this image is reached, the measurer takes his/her fingers off the tension knob and records the IOP reading along with the date and time of day in the source document.

Appendix C. List of Abbreviations

Abbreviation	Definition
AE	adverse event
BCDVA	best-corrected distance visual acuity
CI	confidence interval
DED	dry eye disease
eCRF	electronic case report form
EDS-VAS	Eye Dryness Score - Visual Analog Scale
FWER	family-wise error rate
IES	intercurrent event(s) strategy
IOP	intraocular pressure
ITT	intent-to-treat
IxRS	interactive response system
MD	multidose
MedDRA	Medical Dictionary for Regulatory Activities
MMRM	mixed-effects model repeated measures
NATF	novel artificial tear formulation
NCI	National Cancer Institute
NEI	National Eye Institute
OD	right eye
OHT	ocular hypertension
OS	left eye
OSDI	Ocular Surface Disease Index [®] Questionnaire
OTC	over-the-counter
РР	per-protocol
РТ	preferred term
SAE	serious adverse event
SAP	statistical analysis plan
SD	standard deviation
SoA	schedule of activities
SOC	system organ class
TBUT	tear break-up time
TEAE	treatment-emergent adverse event
TESAE	treatment-emergent serious adverse event

Abbreviation	Definition
VAS	visual analog scale
VS	versus
WHO	World Health Organization

Appendix D. Changes to Protocol-planned Analyses

There are no changes from the protocol-planned analyses.

Electronic Signatures

User	Date	Justification
	02-Aug-2021 20:44:38 (GMT)	Document Originator Approval
	04-Aug-2021 19:44:44 (GMT)	NC - Study Director Approval
	02-Aug-2021 22:16:07 (GMT)	Subject Matter Expert Approval
	03-Aug-2021 21:36:05 (GMT)	Manager Approval

TITLE PAGE

Protocol 2007-301-005

A Multicenter, Single-masked, Randomized Study to Compare the Efficacy and Safety of a New Artificial Tear Formulation (011516X) with Systane[®] Ultra Multidose for 90 Days in Participants with Dry Eye Disease

PER-PROTOCOL ANALYSES DATA EXCLUSION ALGORITHM

Draft: 06-Aug-2021

Confidentiality Statement

Confidentiality Statement

This document is the property of AbbVie, Inc. and may not, in full or part, be passed on, reproduced, published, distributed to any person, or submitted to any regulatory authority without the express written permission of AbbVie, Inc. AbbVie Optive Super

HISTORY OF CHANGE

Amendment: Not applicable

Date	Description of Change(s)
06-Aug-2021	Initial version (Approved)

2007-301-005 Per-Protocol Analyses Data Exclusion Algorithm

1 Introduction

This document is written to detail the algorithms used to define data exclusions from the per-protocol analysis in the 2007-301-005 Amendment 2 and statistical analysis plan (SAP) Amendment 1.0.

The per-protocol (PP) population is defined in SAP section 4.0. The PP analysis will be implemented on the primary efficacy endpoint only. The PP population will consist of participants who contribute data to the PP analysis after implementing the data exclusion algorithms specified in this document. PP population will come from ITT population who are treated. Data from the participants with a protocol deviation that is deemed to affect primary efficacy assessment from a study visit will be excluded from the PP analysis for that study visit.

2 Algorithms to Define Data Exclusion for PP Analysis

2.1. General Rules

Each participant was randomized to receive either 011516X or Systane Ultra Multidose (MD) treatment. Algorithms for data exclusion from PP analysis are defined for primary efficacy analysis of change from baseline in total ocular staining score data of the study eye at Day 90. The algorithm will be applied to all total ocular staining score data of the study eye that are involved in the primary efficacy analysis including that the data from baseline (Day 1), Days 7, 30, 60 and 90/Early Exit.

2.2. Ocular Staining Measurement

Ocular staining measurements are conducted at all study visits for cornea and conjunctiva, and the change from baseline on total staining score at Day 90 is defined as primary efficacy endpoint. Same analysis windows for ITT analysis specified in Statistical Programming Plan will be used in PP analysis.

However, total ocular staining score at Day 90 will use the study visit window of Day 75 to 105 and all ocular staining data collected outside the analysis visit window will either be mapped to earlier visits or be excluded from PP analysis.

2.3. Prohibited Concomitant Medications

Data from the study visits in which ocular staining is potentially affected by prohibited concomitant medications will be considered exclusive for PP analysis. The general rules for total staining data exclusion from PP analysis are provided in protocol deviation requirement specification (PDRS) under code CM-01. The data to be excluded from PP analysis will be stated in the comment field of protocol deviation management tool (PDMT).

2.4. Ocular Concurrent Procedures

Data from the study visits in which ocular staining is potentially affected by ocular concurrent procedures will be considered exclusive for PP analysis. PDRS will provide the category of the PP exclusion under code CP-100. The data to be excluded from PP analysis will be stated in the comment field of PDMT.

Abbvie **Optive** Super

2.5. Inclusion Criteria of Baseline Total Ocular Staining Score

Protocol inclusion criteria requires patients to have baseline total staining score of between 6 and 43 with corneal staining score of 5 to 19 and conjunctival staining score of 1 to 24. If a patient's baseline staining score of cornea and conjunctiva in study eye is outside of inclusion criteria, the study eye baseline and all follow up visit total staining score data will be excluded from PP analysis.

2.6. Other Protocol Deviations Impacting Total Staining Measurement Total staining data will be excluded according to Table 2.6-1 for the following protocol deviations.

Protocol Deviation Code/Category	Description	Excluding Period
SI-02: Dosed with wrong study intervention (ICH)	Participant was not dosed with the assigned study intervention label ID	All data during period not dosed with the assigned study intervention label ID will be excluded from the PP analysis.
SI-400: Study Intervention - Reported incorrect dosing for more than 10 days	Participant reported incorrect dosage of study intervention for more than 10 days	All data during incorrect dosing period will be excluded from the PP analysis.
SP-200: Primary efficacy study procedure – not performed per protocol	Corneal and/or Conjunctival Staining was not performed per protocol at Baseline, Days 7, 30, 60 and/or 90 that may impact subject safety or primary efficacy analysis	All total staining score at the procedure date will be excluded from the PP analysis
EC-01: Prior /concurrent clinical study experience	Are currently enrollment in an investigational drug or device study or participation in such a study within 30 days of entry into this study at the Screening (Day -7) visit	All data will be excluded from the PP analysis.

Table 2.6-1 Protocol Deviation Impacting Total Staining Score

Data Exclusion Reasons and Codes 3

The reasons and codes for total staining data being excluded from PP analysis is summarized below (Table 3-1).

Exclusion Reason	Exclusion Code	Affected Analysis Visit and Description
Ocular staining measurement	A100	All affected visits
Prohibited Concomitant Medications	B100	All affected visits
Ocular concurrent procedures	C100	All affected visits
Baseline total staining	D100	Baseline
Protocol Deviation on dosed with wrong study intervention (SI-02)	E100	All affected visits
Protocol Deviation on study intervention – reported incorrect dosing more than 10 days (SI-400)	E101	All affected visits

Т

Abbvie Optive Super

Protocol Deviation on primary study efficacy procedure – not performed per protocol (SP-200)	E102	All affected visits
Protocol Deviation on prior /concurrent clinical study experience (EC-01)	E-103	All visits

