#### **Overall Rationale for the Amendment:**

The rationale for changes implemented in Protocol Amendment 2 is to clarify inclusion and exclusion criteria such that there are no corneal staining scores that could potentially conflict, and to remove an error related to OSDI scores.

Section Number and Name	Description of Change	Brief Rationale
Section 5.1 Inclusion Criteria, Inclusion Criterion 2.01	Added need not be the same eye at Screening and Baseline	Clarification
Section 5.1 Inclusion Criteria, Inclusion Criterion 2.02	Added need not be the same eye at Screening and Baseline or the same eye that meets Inclusion Criterion 2.01	Clarification
Section 5.2 Exclusion Criteria, Exclusion Criterion 1.02	Removed the lower bound of < 5 for the total cornea staining score, and changed application of the criterion from one or both eyes to either eye	Clarification to prevent potential corneal staining scores from conflicting with inclusion criterion 2.01
Section 8.1.3.5 Ocular Surface Disease Index Questionnaire	Removed sentence that reiterated entry criteria related to the OSDI score and contained an error (> 65)	Clarification to avoid unnecessarily repeating entry criteria language

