#### 5.1. Inclusion Criteria

Participants are eligible to be included in the study only if all of the following criteria apply:

1.	Age
1.01	Participant must be ≥ 18 years of age
2.	Type of Participant and Disease Characteristics
2.01	At the Screening (Day -7) and Baseline (Day 1) visits, at least 1 eye must qualify with both of the following ocular staining scores:
	• Corneal staining score of ≥ 0 to ≤ 4 in each of the 5 zones with a total of ≥ 5 to ≤ 19 based on the modified NEI grading scheme (score range = 0 to 5; graded in 5 zones of the cornea for a total score range of 0 to 25)
	• Conjunctival staining score of $\geq 0$ to $\leq 4$ in each of the 6 zones with a total of $\geq 1$ based on the modified NEI grading scheme (score range = 0 to 5 per zone)
	(Need not be the same eye at Screening and Baseline)
2.02	At the Screening (Day -7) and Baseline (Day 1) visits, have 3 consecutive TBUT tests of $\leq$ 10 seconds in at least 1 eye
	(Need not be the same eye at Screening and Baseline or the same eye that meets Inclusion Criterion 2.01)
2.03	At the Screening (Day -7) and Baseline (Day 1) visits, have a Current Symptom Survey total mean score of $\geq 25$
2.04	At the Screening (Day -7) visit, have an OSDI total score of $\geq$ 23; and at Baseline (Day 1) visit, have an OSDI total score of $\geq$ 18, with no more than 3 responses answered as not applicable (N/A)

2.05	Have used an artificial tear product for DED within 6 months of the Screening (Day -7) visit		
2.06	Have ability/agreement to continue to wear existing current spectacle correction during the study period (if applicable)		
2.07	Have corrected distance visual acuity of at least 20/32 Snellen equivalent in each eye using the 3-meter LogMar chart, with current correction (if necessary) at Screening (Day -7) visit		
2.08	If using any form of topical ophthalmic cyclosporine (ie, RESTASIS®) or lifitegrast 5% ophthalmic solution (Xiidra®), participants must be using the drops for $\geq$ 90 days prior to the Screening (Day -7) visit and plan to continue without change for the duration of the study		
3.	Sex		
3.01	Male or female		
4.	Contraceptives		
4.01	A female participant is eligible to participate if she is not pregnant (ie, has a negative in-office urine pregnancy test at Screening [Day -7] and does not verbally report pregnancy at the Day 1 [Baseline] visit; see Appendix 6), is not breastfeeding, and at least 1 of the following conditions applies:		

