## **5.2.** Exclusion Criteria

Participants are excluded from the study if any of the following criteria apply:

1.	Medical Conditions		
1.01	Have uncontrolled severe systemic disease that, in the assessment of the investigator, would put safety of the participant at risk through participation, or which would prevent or confound protocol-specified assessments (eg, hypertension and diabetes, Sjögren's syndrome, rheumatoid arthritis, systemic lupus erythematosus, immunodeficiency disease, etc.)		
1.02	At the Screening (Day -7) or Baseline (Day 1) visits, either eye has		
	• Corneal staining score of 5 in any of the 5 zones or a total score of > 19 based on the modified NEI grading scheme (score range = 0 to 5; graded in 5 zones of the cornea for a total score range of 0 to 25)		
	or		
	• Conjunctival staining score of 5 in any of the 6 zones based on the modified NEI grading scheme (score range = 0 to 5 per zone)		
1.03	Participant has worn contact lenses in the last 90 days prior to the Screening (Day -7) visit and/or participant anticipates contact lens wear during the study		
1.04	Have any scheduled or planned systemic surgery or procedure during the study, which in the investigator's opinion, may impact the participant's study participation		

1.05	Presence of 1 or more of the following ocular conditions:			
	Active ocular infection or non-keratoconjunctivitis sicca (KCS) ocular inflammation			
	Active ocular allergy			
	History of recurrent herpes keratitis or active disease within 6 months prior to the Screening (Day -7) visit			
	Corneal disorder or abnormality that affects corneal sensitivity or normal spreading of the tear film (except superficial punctate keratitis)			
	• Severe blepharitis or obvious inflammation of the lid margin, which in the judgment of the investigator, may interfere with the interpretation of the study results			
	Keratoconjunctivitis sicca secondary to the destruction of conjunctival goblet cells, such as occurs with vitamin A deficiency or scarring such as that with cicatricial pemphigoid, alkali burns, Stevens-Johnson syndrome, trachoma, or irradiation			
	Substantial non-KCS keratitis with overlying corneal stain or other significant corneal findings not directly related to DED; in addition, participants with DED signs/symptoms (eg, filamentary keratitis) of a severity where topical monotherapy with an artificial tear would be inappropriate			
2.	Prior/Concomitant Therapy			

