## 6.3. Measures to Minimize Bias: Randomization and Masking

This study will use a 1:1 treatment allocation to 011516X:Systane Ultra MD, with a central stratification by Day 1 (Baseline) total ocular staining score in the study eye (mild/moderate = score of 6 to 25 vs severe = score of 26 to 43). The study eye is defined as the worst eye based on total ocular staining score at Day 1 (Baseline). If both eyes have the same total ocular staining score, the right eye will be designated as the study eye.

Prior to initiation of study intervention, each participant who provides informed consent will be assigned to a participant number through an automated IxRS that will serve as the participant's identification number on all study documents. Participant numbers will be assigned in ascending order across all sites and should not be omitted or reused.

At the end of the Screening (Day -7) visit, all eligible participants will receive a run-in medication kit (REFRESH PLUS) for use during the 7-day run-in period. Sites will dispense the run-in medication kit according to the IxRS instructions.

At the end of the Day 1 (Baseline) visit, all eligible participants will be stratified by their Day 1 (Baseline) study eye total ocular staining score and be randomly assigned to 1 of 2 treatment arms in a 1:1 ratio based on a randomization scheme prepared by Allergan Biostatistics. This will require the delegated site personnel to enter the participant's Screening Visit (Day -7) and Baseline (Day 1) total corneal and conjunctival staining scores of each eye directly into IxRS. IxRs will then determine which eye is the study eye and assign the participant to a stratification group and a treatment arm, thus providing the site with the specific study intervention kit assignment. Sites will dispense study intervention according to the IxRS instructions.

Sites will also need to access the IxRS at the Days 30 and 60 visits to obtain a study intervention kit (30-day supply) number to dispense to the participant. Sites will receive the IxRS confirmation notifications for each transaction. All notifications are to be maintained with the study source documents.

In addition, sites will need to access IxRS to "complete" the participant at Day 90 or to "discontinue" the participant if they exit the study early.

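### The per-protocol baseline-staining rule tests the study eye against a range the protocol requires in only one eye, so it drops eligible participants who have no deviation

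*SAP*

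**What the plan says.** The algorithm's Section 2.5 opens "Protocol inclusion criteria requires patients to have baseline total staining score of between 6 and 43", split into cornea 5 to 19 and conjunctiva 1 to 24. Its exclusion sentence then reads, in part, "baseline staining score of cornea and conjunctiva in study eye is outside of inclusion criteria, the study eye baseline and all follow up visit"; the data so covered leave the PP analysis.

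The protocol words the criterion differently. Under Inclusion Criterion 2.01 (Section 5.1), "at least 1 eye must qualify with both of the following ocular staining scores", and the qualifying eye may change between visits: "Need not be the same eye at Screening and Baseline".

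Exclusion Criterion 1.02 (Section 5.2) applies to either eye but sets only upper limits. For the cornea it reads "Corneal staining score of 5 in any of the 5 zones or a total score of > 19"; for the conjunctiva it bars a 5 in any zone. Amendment 2 took the lower corneal bound out of 1.02, giving as its reason "Clarification to prevent potential corneal staining scores from conflicting with inclusion criterion 2.01".

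Protocol Section 6.3 makes the eye with the higher Day 1 total the study eye, the right eye if tied. The choice is automatic: "IxRs will then determine which eye is the study eye and assign the participant to a stratification group and a treatment arm". Nothing there requires the chosen eye to be one that met 2.01.

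SAP Section 4.0 limits PP exclusion to participants with protocol deviations affecting the primary efficacy analysis. The algorithm's own introduction also ties exclusion to a deviation. SAP Section 8.3.3 makes the PP analysis the only planned sensitivity analysis of the primary endpoint.

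**The concern.** The rule turns a condition on at least one eye into a condition on one particular eye and still calls it a protocol criterion. The study eye is chosen on total score alone. An eye with little corneal staining but much conjunctival staining can therefore outrank the eye that qualified the participant, and so can an eye with corneal but no conjunctival staining. Such a participant met every entry criterion, so there is no deviation to justify exclusion.

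For the cornea, the rule also brings back, for the study eye, the floor that Amendment 2 removed from Exclusion Criterion 1.02.

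What is at stake is the meaning of the PP set in a noninferiority trial. A report would describe it as participants without relevant deviations. In fact it would also lack an eligible group defined by low corneal or absent conjunctival staining in the analysed eye.

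**Working it through.** **1. Reproduce the stated range.** From Inclusion Criterion 2.01: minimum total 5 + 1 = 6; conjunctival maximum 6 zones × 4 = 24; maximum total 19 + 24 = 43. The figures in Section 2.5 are right. The eye they are applied to is not the one in the protocol.

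**2. Counterexamples (cornea + conjunctiva, Day 1).**

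| Right eye | Left eye | Meets 2.01 | Study eye | Result under Section 2.5 |
|---|---|---|---|---|
| 5 + 1 = 6 | 4 + 14 = 18 | right eye | left | dropped, cornea 4 < 5 |
| 5 + 1 = 6 | 8 + 0 = 8 | right eye | left | dropped, conjunctiva 0 |

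With no zone scored 5, neither participant breaches Exclusion Criterion 1.02. Both are eligible.

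**3. Which limits conflict.** In an eligible participant the qualifying eye totals at least 6, so the study eye does too. Exclusion Criterion 1.02 holds both eyes to cornea ≤ 19 and conjunctiva ≤ 24. The study-eye total is therefore always 6 to 43, and only the component floors can fail. Both floors cannot fail together, because cornea ≤ 4 with conjunctiva 0 totals at most 4, which is below 6.

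**4. Count the pairs within the upper limits.** Each eye has 20 × 25 = 500 possible score pairs, of which 15 × 24 = 360 qualify and 140 do not. All two-eye pairs: 500² = 250,000. Neither eye qualifies: 140² = 19,600. Eligible: 250,000 − 19,600 = 230,400.

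Let the study eye be non-qualifying with total t, and let W(t) be the number of arrangements in which the fellow eye qualifies with a total that does not outrank it. This counts right and left assignment, with ties going to the right eye. Then W(t) = (t − 5)² for t = 6 to 20, and W(t) = 255, 285, 315, 345, 375, 405, 435, 465 for t = 21 to 28.

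- Conjunctiva 0 (cornea 6 to 19): the sum of m² for m = 1 to 14 is 14 × 15 × 29 / 6 = 1,015.
- Cornea < 5, t = 6 to 20, five corneal values each: 5 × (15 × 16 × 31 / 6) = 5 × 1,240 = 6,200.
- Cornea < 5, t = 21 to 24: 5 × (255 + 285 + 315 + 345) = 6,000.
- Cornea < 5, t = 25 to 28, where the ceiling of 24 leaves 4, 3, 2 and 1 corneal values: 1,500 + 1,215 + 870 + 465 = 4,050.

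Cornea < 5 in total: 6,200 + 6,000 + 4,050 = 16,250. Eligible pairs removed: 16,250 + 1,015 = 17,265. Study-eye totals run from 6 to 28. In the severe stratum (26 or more): 1,215 + 870 + 465 = 2,550. In the mild/moderate stratum: 17,265 − 2,550 = 14,715. A direct enumeration gives the same counts.

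**5. Test the replacement rule over the full scale** (cornea 0 to 25, conjunctiva 0 to 30; 806² = 649,636 pairs). The replacement excludes when neither eye met 2.01 or the study eye is above an upper limit.

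| Pairs | Number | Current rule | Replacement |
|---|---|---|---|
| Neither eye qualifies | 198,916 | all removed | all removed |
| Study eye over an upper limit, fellow eye qualifies | 189,390 | all removed | all removed |
| Eligible, study eye below a floor | 17,265 | all removed | none removed |

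The rules differ only on the eligible pairs. The second condition is needed: a test of 2.01 alone would miss all 189,390 pairs in the second row. The enumeration uses totals and does not model zone scores.

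**6. Precision.** SAP Section 2.4 inputs: margin 2.3, SD 6.01, 170 per arm, 1-sided 2.5%, no true difference. Noncentrality is 2.3 / (6.01 × √(2/170)) = 3.53, which gives power 94.0% by noncentral t. The documents give no loss rate. For an assumed 1% loss (168.3 per arm; about 4 of 400 randomised) power is 93.8%. For 5% (161.5 per arm; about 20 of 400) it is 92.9%.

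**The case against.** The strongest case is that the consequence is minor. PP is a sensitivity analysis of one endpoint. The filter uses a score taken before randomisation, so losses balance between arms in expectation. Power stays above the planned 90% at the assumed losses. The pair counts weight every score combination equally and say nothing about how often such eyes occur. All of this stands, and it limits the weight of the point.

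A second argument is that a sponsor may reasonably want the analysed eye itself to be in range, since the endpoint is measured there. The algorithm also says PP membership is whatever remains after its rules are applied. The restriction is a legitimate choice. But the text presents it as a protocol inclusion criterion, which it is not, and the same introduction bases exclusion on a deviation. The wording has to change either way.

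Third, the rule could be read as requiring cornea and conjunctiva both to be out of range. On that reading no eligible pair is removed. It is a strained reading: a study eye with cornea 22 and conjunctiva 10 would then stay in the PP set, although a separate range is given for each component.

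Fourth, the replacement tests 1.02 only in the study eye and only on Day 1, whereas the protocol applies it to either eye and also at Screening. That is true. The replacement stops over-exclusion without adding exclusions the current rule does not make. Extending it is the sponsor's decision.

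**Conclusion.** The concern holds. Read in the ordinary way, with either component out of range counting as a failure, Section 2.5 removes eligible participants who have no deviation. That contradicts SAP Section 4.0 and the algorithm's introduction. The fault is confined to the two lower limits, cornea below 5 and conjunctiva 0 in the study eye. The rule does catch every Day 1 failure of 2.01.

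The size in participants is unknown. The 17,265 pairs show that the conflict is not confined to one odd case, but they are not a prevalence, and the 1% to 5% loss is an assumption. The primary intent-to-treat analysis, the study-eye choice and the strata are unaffected. This should be corrected because it decides who enters the only sensitivity analysis of the noninferiority result; it does not threaten that result directly.

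**What to change.** Replace the operative sentence of Section 2.5 with a rule to this effect:

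> If, at Day 1, neither eye met Inclusion Criterion 2.01, or the study eye met Exclusion Criterion 1.02, all total staining data for the study eye, at baseline and every follow-up visit, are left out of the PP analysis. An eye does not meet 2.01 if its corneal or its conjunctival score, by zone or in total, is out of range.

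Amend the first sentence to say that the protocol requires the range in at least one eye.

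Alternatively, if the sponsor wants the analysed eye to be in range, keep the test, label it an analysis restriction rather than an inclusion criterion, and reconcile it with the PP definition in SAP Section 4.0.

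As a clerical matter, the D100 row of Table 3-1 lists only the baseline visit and can be aligned with the text of Section 2.5. With the baseline removed no change score exists at any visit, so the result does not depend on it.

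The cost is two sentences and, optionally, one table cell. Per-eye scores are already collected and entered into the IxRS. The protocol, randomisation, strata and intent-to-treat analysis do not change. The edit belongs before database lock; the documents give no lock date, so this assumes lock has not yet occurred.
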